Tolerability and safety: Participants' weight, height, body mass index, age, blood pressure, temperature, respiration rate, and pulse rate will be recorded at each study visit to monitor for adverse events and asymptomatic illnesses that may impact study results. Vitals will be collected at baseline, 7 hours post-Shoden administration, and at the end of each baseline visit. At the beginning of each baseline visit, participants will complete an electrocardiogram (ECG) and the Geriatric Depression Scale-15. Four teaspoons of blood (20 ml) will be collected for safety labs (CBC, CMP, urinalysis, TSH, serum total testosterone). ECG will be repeated 7 hours post-intervention to assess for cardiac changes. One teaspoon (5 ml) will be collected for a repeat CMP at 10 hours post-intervention to evaluate kidney and liver function. Participants will be interviewed and administered a standardized multi-system adverse events questionnaire at the beginning and end of each baseline visit. This visit is expected to take 13 hours a total of 175 mL of blood will be collected.

If the baseline CBC shows hemoglobin or hematocrit levels below what is recommended by the FDA for blood donation, the visit will be halted immediately. Participants will be asked to stay for 2.5 hours after the study agent has been administered to assess for acute side effects. Two and a half hours was chosen because common withanolides have reached their C_{MAX} by this time based on a previous PK study using Shoden®.⁸⁰ The end-of-visit adverse events questionnaire will be administered by phone and missed safety evaluations (7-hour ECG and vitals, 10-hour CMP, 12-hour vitals) will be collected at the 24-hour visit. After the 24-hour visit, the participant will be withdrawn from the study.

If study staff have difficulties collecting blood samples for any reason, the decision may be made to halt the visit. Participants will be asked to stay for 2.5 hours after the study agent has been administered to assess for acute side effects. If the visit ends before the 7-hour mark, the end-of-visit adverse events questionnaire will be administered by phone and missed safety evaluations (7-hour ECG and vitals, 10-hour CMP, 12-hour vitals) will be collected at the 24-hour visit. Participants will be allowed to remain on the study if difficulties with blood sample collection were the only reason for halting the study visit early.

I.4.2 24- and 48-Hour Visits

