Participants will return at 24 hours and 48 hours for a single blood collection (two teaspoons (10 ml)) and urine collection. Vitals will be collected. A CMP and ECG may be collected at the 24-hour visit if the baseline visit was halted prior to 7 hours. At the 48-hour visit, the adverse events questionnaire will be administered as the baseline measure for the subsequent four-week period. After the 48-hour visit, participants will be issued a 35-day supply of the appropriate dose of Shoden® (240 or 480 mg), which they will begin taking before bed every day for four weeks. These visits are expected to take 20 minutes. After analyzing the plasma and urine samples for the first two participants, a determination will be made as to whether the 48-hour PK visit is needed for future participants. If no withanolides are detected in plasma or urine at 48-hours, this time point will be eliminated to avoid undue participant burden.

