1.8. REDCap Surveys

Participants will be emailed a link to electronic surveys in REDCap at four time points during the study: during the week prior to each PK visit and during the week prior to each four-week follow-up visit. Participants will complete two surveys at each time point: Pittsburgh Sleep Quality Index (PSQI) and the Perceived Stress Scale (PSS).

I.9. Washout Period

The two study periods will be separated by a 2- to 4-week washout period where the participant will not take the study agent. If the washout period is longer than 21 days, participants will be called at two weeks to assess for delayed side effects.

I.10. Subject participation duration

Including the screening visit, a two to four-week washout period between doses, and an exit phone interview for adverse event monitoring, it will take participants 13 to 14 weeks to complete the study.

Table 1. Schedule of study visits and assessments.

	Screen	PK visit			2-week f/u	4-week f/u	Washout Period	PK visit			2-week f/u	4-week f/u	Final visit +2 weeks
Study Period		1			1	1		2			2	2	
Event	Clinic Visit	0 to 12h	24h	48h	Phone visit	Clinic visit		0 to 12h	24h	48h	Phone visit	Clinic visit	Phone visit
Informed consent	X												
Vitals and biometrics	X	X ⁺	X	X		X		X ⁺	X	X		X	
Health screening	X												
Electrocardiogram (ECG)	X	X [§]	X [°]			X		X [§]	X [°]			X	
CBC*, CMP*, TSH [^] , and UA*	X	X [^]	X [°]			X		X [^]	X [°]			X	
Serum testosterone		X				X		X				X	
Single dose of intervention		X						X					
Single-dose PK blood draws		X	X	X				X	X	X			
Issue 35-day supply of Shoden®				X [#]						X [#]			
Steady state PK blood draw						X						X	
12-hour urine collection		X						X					
Single urine collection		X [¶]	X	X		X		X [¶]	X	X		X	
Collect and count unused capsules						X						X	
Adverse events questionnaire		X [*]		X	X	X		X [*]		X	X	X	X
Cognitive screen (MMSE)	X												
Depression screen (GDS)	X	X [♦]			X	X		X			X	X	X
REDCap surveys		X [▼]				X [▼]		X [▼]				X [▼]	

f/u – follow-up

§ ECG collected prior to Shoden® administration and at 7 hours post-Shoden® administration

* CBC = Complete Blood Count with differential; CMP = Comprehensive Metabolic Panel; UA = Urinalysis

^ CMP collected prior to Shoden® administration and at 10-hours post-Shoden® administration

▲ TSH = Thyroid-stimulating hormone

This will take place at the 24-hour visit if 48-hour visit is eliminated, as described in Section I.4.

¶ Aliquot of baseline urine prior to administration of Shoden®

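### After a blood-draw halt, the 24-hour catch-up applies only before 7 hours, so a halt from 7 to before 10 hours has no clear replacement for the 10-hour CMP

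*Combined protocol and SAP*

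**What the plan says.** Section I.4.1 (Tolerability and safety) sets the test: "One teaspoon (5 ml) will be collected for a repeat CMP at 10 hours post-intervention to evaluate kidney and liver function". A Table 1 footnote agrees ("CMP collected prior to Shoden® administration and at 10-hours post-Shoden® administration"), and section N gives the same time. The repeat ECG is due earlier, at 7 hours.

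I.4.1 lets staff halt a baseline visit if blood sampling proves difficult. For such a halt the catch-up rule opens "If the visit ends before the 7-hour mark, the end-of-visit adverse events questionnaire will be administered by phone" and continues "missed safety evaluations (7-hour ECG and vitals, 10-hour CMP, 12-hour vitals) will be collected at the 24-hour visit". The participant need not leave the trial: "Participants will be allowed to remain on the study if difficulties with blood sample collection were the only reason".

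Section I.4.2 restates the rule for the 24-hour visit: "A CMP and ECG may be collected at the 24-hour visit if the baseline visit was halted prior to 7 hours". A second Table 1 footnote says that an ECG and a CMP will be done at 24 hours when the visit stopped ahead of a 7-hour ECG and CMP. It does not say what happens when the ECG has been done and the CMP has not.

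**The concern.** A 7-hour cut-off suits the ECG and the mid-visit vitals, because both fall due at 7 hours. It does not suit a test due at 10 hours. The catch-up list names the 10-hour CMP, so the protocol means to recover it, yet the trigger leaves out the last three hours in which it can be missed. The reason for the halt is trouble drawing blood, which is when a blood tube is most likely to be lost.

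In each period the 10-hour CMP is the only scheduled CMP between the first dose and the four-week visit. Section C.2.3 reports rare but serious liver injury with other use of this botanical. For 480 mg, the protocol's tolerability evidence is a single administration in 16 participants. A participant in the gap would go on to four weeks of daily dosing without the planned acute check, and staff following I.4.1 or I.4.2 would have no instruction to replace it.

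**Working it through.** The plan states no figure for this gap, so the check compares the rules on one timeline.

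**Inputs**
- Repeat CMP due at 10 h (I.4.1, Table 1 footnote, section N).
- Catch-up trigger after a sampling halt: visit ends before 7 h (I.4.1, I.4.2).
- Post-dose PK draws at 15, 30, 45, 60, 90, 120, 150, 180, 210, 240, 300, 360, 540 and 720 min (I.4.1, Sample collection).
- 12 enrolled, 10 expected to complete, 2 periods (F.1, F.2.1).

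**Rule.** For a halt at h hours after dosing, the CMP has been taken if h ≥ 10, and the catch-up applies if h < 7. The gap is every h for which neither holds: 7 ≤ h < 10.

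| Halt time | 10-hour CMP taken? | Catch-up under I.4.1 and I.4.2? | Result |
|---|---|---|---|
| before 7 h | no | yes | replaced at 24 h |
| 7 h to before 10 h | no | no | no replacement in the body text |
| 10 h or later | yes | not needed | complete |

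**Size of the window.** 10 − 7 = 3 hours. Of the 14 post-dose PK draws, 12 fall before 420 min, 1 falls from 420 to before 600 min (the 540-minute draw), and 1 falls after 600 min (720). So 1 of 14 scheduled draws lies in the gap. This counts draws; it is not a probability of halting.

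**Exposure.** 12 × 2 = 24 baseline visits at most, or 10 × 2 = 20 from the expected completers. No halt rate is given, so no expected number of affected visits can be calculated. In an affected period, post-dose CMPs fall from 2 (10 h and week 4) to 1 (week 4).

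**Blood volume, for the cost of the fix.** The protocol's own total is "This visit is expected to take 13 hours a total of 175 mL of blood will be collected". It reproduces: 10 (pre-dose) + 14 × 10 + 20 (safety labs) + 5 (CMP) = 175 ml. At a halt on the 540-minute draw, 10 + 12 × 10 + 20 = 150 ml has been taken, or 160 ml if that draw succeeded. Adding a 5 ml make-up CMP gives 155 to 165 ml, below 175 ml. The routine 10 ml at 24 hours is drawn in either case.

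**The footnote.** It can be read in two ways. If it means that the 7-hour ECG and the CMP have not both been collected, a halt at 9 hours requires a CMP at 24 hours. If it treats both as 7-hour tests, that halt falls outside it. The first reading conflicts with the limit in I.4.1 and I.4.2; the second conflicts with the 10-hour timing. I.4.2 also says the tests *may* be done, while I.4.1 and the footnote say *will*.

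**After the fix.** If the CMP trigger becomes a halt before the 10-hour CMP is collected, the uncovered window goes from 3 hours to 0.

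**The case against.** The strongest reply is that the footnote already covers the case on an ordinary reading, and that I.4.1 and I.4.2 do not forbid a later make-up CMP. Halting is also discretionary: after a failed draw at 9 hours, staff could keep the participant one more hour for the CMP, which section N lists without any halt condition. These points stand as reasons why the gap will seldom matter. They do not close it, because two body sections give an explicit 7-hour limit and the footnote does not clearly override them.

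The clinical consequence is also limited, and that stands in full. The liver and renal plan in C.2.3 and O.1 rests on the start and end of each period. Section L.2 analyses baseline to week 4. Entry requires normal hepatic and renal values, and adverse event questionnaires remain at 48 hours and two weeks.

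A reader might infer more than the text supports:
- *That four-week dosing is meant to depend on the 10-hour CMP.* No section makes it a condition for dispensing or starting the supply.
- *That the low-hemoglobin paragraph, which gives the same list with no 7-hour condition, shows the condition is a mistake.* That halt is immediate once the baseline CBC is known and carries a 2.5-hour stay, so it would normally end well before 7 hours and would not need the condition.
- *That a failed CMP tube at 10 hours belongs in the count.* It lies outside the 7-to-10-hour window, and a failed tube is not necessarily a halted visit.
- *That vitals are lost too.* I.4.1 already says "Vitals will be collected at baseline, 7 hours post-Shoden administration, and at the end of each baseline visit", and I.4.2 takes them from everyone at 24 hours.

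**Conclusion.** The point holds, as a minor one. For visits halted for blood-draw difficulty, the body text provides no replacement CMP when the halt comes at or after 7 hours and before 10 hours, and the Table 1 footnote does not settle the matter. The trigger does not match the test it is meant to recover.

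The loss is one acute single-dose check per affected visit, with 1 of 14 post-dose PK draws in the window and at most 24 visits. This rests on reading I.4.1 and I.4.2 as written and on staff choosing to stop rather than wait for 10 hours. How often that would happen cannot be estimated from the documents. The finding concerns the completeness of acute safety monitoring; the PK endpoints, the baseline and week-4 labs, the L.2 analysis and the stopping rule are untouched.

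**What to change.** Use one rule in I.4.1, I.4.2 and the Table 1 footnote: if a visit is halted before the 10-hour CMP has been collected, a CMP *will* be collected at the 24-hour visit, and the ECG will be made up there only if the 7-hour ECG was missed. Replace *may* in I.4.2. The 7-hour condition can stay for giving the adverse event questionnaire by phone.

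The cost is a wording change in two sections and one footnote and, in a rare visit, 5 ml more blood at 24 hours. The draw may again be difficult in that participant. A 24-hour value is also not a 10-hour value, but the protocol already accepts that substitution for earlier halts. Any listing of acute CMP results should show the actual collection time.

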Safety, tolerability, and pharmacokinetics of an oral *Withania somnifera* product in older adults

NCT06171724

Version Date: 10.10.2024

Title: Safety, tolerability, and pharmacokinetics of an oral *Withania somnifera* product in older adults

Principal Investigator: [name], ND, MS [contact]

Co-Investigators/staff: [name] (Clinical Investigator) [contact]
[name] (Co-Investigator) [contact]
[name] (Study staff)
[name] (Study staff)

A. OBJECTIVES

A.1. Purpose

The purpose of this pilot study is to measure the oral absorption and pharmacokinetics (PK) of compounds from two doses of a standardized *Withania somnifera* extract product (Shoden®) in healthy older adults. Compound levels will be measured in human plasma and urine over 48 hours after acute oral administration and after four weeks' use of Shoden®. Peak exposure and time, total exposure, half-life, and urinary excretion of compounds will be calculated. These data will be used to inform decisions on the dosage and dosing frequency for future phase 1 and phase 2 clinical trials.

A.2. Primary goal

To determine the oral bioavailability and PK of withanolides from two doses of a *Withania somnifera* product (Shoden®) in healthy older adults following single administration and after four weeks' use.

A.3. Endpoints

- Primary endpoints:
 - Peak exposure and time (C_{max} , T_{max}) and total exposure (AUC_{0-t} , $AUC_{0-\infty}$) of withanolides from Shoden® in human plasma after a single administration.
- Secondary endpoints:
 - Half-life ($t_{1/2}$) of withanolides from Shoden® to help determine dosage intervals.
 - Urinary excretion of withanolides from Shoden®
 - Steady-state levels of withanolides after four weeks' use.
 - Tolerability and safety of Shoden® following single administration and after four weeks' use.
 - Feasibility of assessing sleep- and stress-related outcomes remotely using REDCap surveys.

B. SPECIFIC AIMS

Aim 1: Evaluate the oral absorption and PK of selected withanolides from Shoden® in older adults.

- **Hypothesis:** Selected withanolides will be detectable in the plasma and urine at both doses of Shoden®, with significantly greater plasma levels achieved at the 480 mg dose.

Aim 2: Assess the safety and tolerability of Shoden® in older adults.

- **Hypothesis:** A single administration and four weeks' use of Shoden® at 240 and 480 mg per day will be well tolerated and produce no severe adverse events.

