1.4.1. Baseline Visit (0-12hr)

Visit Timing: For the first study period, Baseline Visit 1 will occur a minimum of three days after the screening visit to allow for review of laboratory results and scheduling of appropriate facilities. For the second study period, Baseline Visit 2 will occur a minimum of two weeks (and not more than three weeks) after the four-week follow-up visit for the first study period.

Sample collection: Participants will be asked to fast for 10-12 hours, excluding water, the night before each baseline visit in an attempt to standardize gastrointestinal transit time and minimize delayed absorption of the study intervention due to the presence of food. Participants will be reminded during the pre-visit reminder call to arrive at the visit well-hydrated to facilitate blood collections. Study staff will place a peripheral intravenous catheter in the participant's arm or hand to allow for serial plasma specimen collection. Prior to administration of Shoden®, a baseline plasma sample of two teaspoons (10 ml) will be collected through the catheter using a syringe and transferred immediately into a heparinized Vacutainer tube. The participant will then be administered two capsules of Shoden® (240 or 480 mg total) on an empty stomach in the presence of study staff to ensure compliance. Participants will be asked to abstain from food and drink (excluding water) for the first two hours following consumption of Shoden® capsules to allow for transition into the small intestine and absorption. If signs of hypoglycemia are present, participants will be allowed to consume a high glycemic food and monitored for improvement. Participants will be provided water at the visit and will be encouraged to drink four 16-ounce cups of water over the 12 hours to maintain good hydration status. Serial blood samples (two teaspoons (10 ml) per sample) will be collected through a peripheral intravenous catheter, at 15, 30, 45, 60, 90, 120, 150, 180, 210, 240, 300, 360, 540, and 720 minutes after dosing. A baseline urine sample and a 12-hour pooled urine collection will be obtained to measure excretion of WS metabolites.

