1.6. Four-Week Follow-Up Visit

Participants will be asked to fast for 10-12 hours, excluding water, the night before each four-week follow-up visit in order to collect fasting glucose as part of the CMP. A single blood sample (two teaspoons (10 ml)) and a urine sample will be collected to assess steady state plasma levels and excretion of WS compounds. Returned capsules will be counted to assess for adherence. Participants will have an ECG and blood and urine samples will be sent for safety labs (CBC, CMP, urinalysis, TSH, serum total testosterone, serum DHEA-S). The Geriatric Depression Scale-15 will be administered. At the four-week follow-up visit for the second study period, participants and investigators will be queried as to their perception of the dose sequence administered. This visit is expected to take 45-60 minutes.

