Upon enrollment, each participant will obtain a unique identification number. This number will be associated with all specimens and data collected from that participant. Following the collection of whole blood from the participant, a trained member of the study team will transfer the blood to the specified vacutainer tubes. Blood will be centrifuged in the CTSC's laboratory to separate the plasma for analysis. The isolated plasma will be transferred into labeled tubes and placed on ice until transported by a member of the study team via a sealed Styrofoam cooler labeled with biohazard to the [name] Lab (Richard Jones Hall, OHSU). The plasma and a 50mL aliquot of the urine specimens will be stored in labeled boxes in [name] -80°C freezer.

Electronic data from case report forms and specimen analysis will be entered in REDCap. Analyzed data will be stored in an OHSU approved cloud storage (OneDrive). Only study team members will be granted access to the REDCap database or OneDrive with access specific to their role in the project. Paper records including participant contact information, telephone screening responses, consent forms, electrocardiogram reports, lab results, and paper case report forms will be stored in participant-specific binders, kept in a locked cabinet at the Parkinson's Center of Oregon office suite (Sam Jackson Hall), where [name] is located.

K.3. Sharing of results with participants

All screening laboratory results, performed by the CLIA-certified OHSU Core Laboratory, will be shared with the participant through their medical record. If a screening result is found abnormal

(an incidental finding), the participant will be instructed to share their result with their primary care provider. Electrocardiograms (ECGs) will be performed at the screening visit, PK visits, and four-week follow-up visits. If the ECGs are found to be abnormal, the participant will be instructed to share their result with their primary care provider. As there will be no additional laboratory assessments with clinical implications beyond the screening visit, no results from the study will be shared with the research participant or their provider(s).

K.4. Data, Specimen banking, and Repository Procedures

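### Timed urine is collected only for 0–12 h, so the later single samples, including the week-4 sample meant to assess excretion, cannot give an amount or rate excreted

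*Combined protocol and SAP*

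**What the plan says.** A.1 sets the scope: "Compound levels will be measured in human plasma and urine over 48 hours after acute oral administration and after four weeks' use of Shoden". A separate sentence in A.1 adds that urinary excretion is among the quantities to be calculated. A.3 lists "Urinary excretion of withanolides from Shoden" as a secondary endpoint, with no parameter, unit or time window.

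The collections are:

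- **0–12 h (Section I.4.1):** "A baseline urine sample and a 12-hour pooled urine collection will be obtained to measure excretion of WS metabolites".
- **24 h and 48 h (Section I.4.2):** "Participants will return at 24 hours and 48 hours for a single blood collection (two teaspoons (10 ml)) and urine collection". The visits are expected to last 20 minutes, and no take-home container is described.
- **Week 4 (Section 1.6):** alongside one blood sample, "a urine sample will be collected to assess steady state plasma levels and excretion of WS compounds".

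Table 1 marks the 12-hour urine row only in the 0 to 12 h column of each period. The row "Single urine collection" is marked for the pre-dose aliquot, 24 h, 48 h and the four-week visit.

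On handling, K.2 says "The plasma and a 50mL aliquot of the urine specimens will be stored in labeled boxes". It does not mention recording the total volume. L.1 states that urine will be assayed, but its formulas and tests cover plasma parameters only.

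**The concern.** Excretion is an amount: concentration multiplied by volume, summed over contiguous timed intervals. A single sample with no known collection interval and no volume gives a concentration that depends on how dilute the urine was. A creatinine ratio would partly correct for dilution, but no urine creatinine is planned.

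The sharpest mismatch is at week 4, where one urine sample is assigned a purpose (excretion at steady state) that it cannot serve as scheduled. After the single dose, an amount can be obtained for 0–12 h and for nothing later. Even that amount needs the total pool volume, which the protocol does not ask anyone to record and which cannot be reconstructed once the pool has been discarded.

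At stake is one secondary endpoint: it could be reported as excretion when most of the underlying samples are uncorrected concentrations.

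**Working it through.** The plan gives no figure for urinary excretion, so there is none to reproduce. The check has two parts.

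**1. Timed coverage.** The amount excreted over a window is Ae = Σ (concentration × volume) over contiguous timed intervals, so only timed, pooled urine counts.

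- Single dose: the window in A.1 is 48 h and the timed urine is the 12 h pool. Coverage = 12/48 = 25%. Nothing is collected over 12–24 h or 24–48 h as an interval.
- Steady state: dosing is once daily before bed (Section I.4.2), so the dosing interval is 24 h. Timed urine at week 4 is 0 h. Coverage = 0/24 = 0%.

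Intervals of 12–24 h and 24–48 h with recorded volumes would bring single-dose coverage to 48/48 h. A 24 h collection at week 4 would bring that to 24/24 h.

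**2. How much excretion might fall after 12 h.** The documents give no half-life (T); estimating it is itself a secondary endpoint. The values below are therefore assumptions. With first-order elimination and instantaneous absorption, the share of 0–48 h excretion falling after 12 h is

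share = 1 − (1 − 0.5^(12/T)) / (1 − 0.5^(48/T)).

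Examples:

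- T = 6 h: 1 − (1 − 0.25)/(1 − 0.0039) = 0.247.
- T = 12 h: 1 − (1 − 0.5)/(1 − 0.0625) = 0.467.

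The last column repeats the calculation for a one-compartment model with an assumed absorption rate constant ka = 1 per hour. With k = ln 2/T, the cumulative fraction excreted by time t is then 1 − (ka·e^(−kt) − k·e^(−ka·t))/(ka − k).

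| Assumed half-life | Instantaneous absorption | ka = 1/h |
|---|---|---|
| 2 h | 1.6% | 2.4% |
| 4 h | 12.5% | 15.1% |
| 6 h | 24.7% | 27.9% |
| 8 h | 34.3% | 37.6% |
| 12 h | 46.7% | 49.7% |
| 24 h | 60.9% | 63.4% |

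So the 0–12 h pool captures nearly all of the 48 h amount if half-lives are about 2 h, and about half of it if they are about 12 h. The documents do not allow a choice between these cases, and the answer may differ by withanolide.

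**The case against.** Much can be said for the plan, and several points stand.

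- **No explicit promise of cumulative 48 h excretion.** A.1 ties the 48 hours to compound levels and mentions calculated excretion in a separate sentence without a window; A.3 names no window either. In the single-dose phase, Section I.4.1 links excretion only to the 12 h pool. A reader might infer that the whole endpoint is lost. It is not: the 0–12 h amount is available if the volume is recorded.
- **The stated hypothesis is met by single samples.** Aim 1 asks of urine only that withanolides be detectable. Section I.4.2 likewise uses the 48 h urine for detection, to decide whether that time point is kept.
- **No urine comparison is planned.** L.1 tests dose differences in plasma parameters only. A reader might infer that a dose comparison or a single-dose versus week-4 comparison will be driven by hydration. No such urine test is specified and the documents give no figures for dilution, so that goes too far. The water encouraged during the baseline visit does not bias an amount computed from pooled volume, and week 4 repeats the overnight fast with water allowed.
- **Silence on volume is not proof that it goes unrecorded.** This is a single-site study, and staff may well measure it. On its own this is missing detail.
- **Section I.4.2 is ambiguous alone.** Its wording could cover an interval collection. Table 1 and Section 1.6 settle that it is a single sample; that this means one void is the natural reading, though the protocol does not use the term.

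None of this supplies an interval, a volume or a creatinine value for the later samples, and Section 1.6 still assigns the week-4 sample to measuring excretion.

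**Conclusion.** The point holds in a limited form. As scheduled, no amount or rate of excretion can be obtained after 12 h or at steady state. The 24 h, 48 h and week-4 samples support detectability and uncorrected concentration only. The coverage figures (12 of 48 h; 0 of 24 h) follow directly from Table 1 and the once-daily dosing and need no assumption.

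The size of what is missed after the single dose is not established. The range of about 2% to 50% of 0–48 h excretion rests on assumed half-lives of 2 to 12 h and a one-compartment model. It should not be read as evidence of a large loss, nor can a small one be taken for granted.

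This affects one descriptive secondary endpoint in a 12-person pilot. The primary plasma endpoints and the Aim 1 detectability hypothesis are untouched. It is a cheap improvement, best made before collection because an unrecorded pool volume cannot be recovered.

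**What to change.** 1. In A.3 and L.1, define the urinary excretion endpoint as the amount of each withanolide excreted over 0–12 h: concentration in the pool multiplied by total pool volume.
2. In I.4.1 and K.2, require the total volume of the pool to be recorded before the 50 mL aliquot is taken.
3. Measure creatinine in the stored urine aliquots. Report the 24 h, 48 h and week-4 samples as detected or not detected, plus analyte/creatinine ratios. Detectability must stay in the report because Aim 1 depends on it.
4. Reword A.1 and Section 1.6 so that these single samples are not described as measuring excretion. The statement in A.1 about levels over 48 hours can stand.

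Fraction of dose excreted should not be required. L.1 admits analytes found only after acid hydrolysis of the product, so a compound in urine may have been formed by deglycosylation and its administered amount is not simply its content in the capsule.

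Timed home collections for 12–24 h and 24–48 h, with recorded volumes, are an option if the sponsor wants excretion to 48 h. They would burden participants and are not needed for the narrower endpoint.

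The cost is a routine creatinine assay on urine already stored, one recorded volume per study period, some rewording, and a narrower stated endpoint. No visit is added.
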